### 3) STUDY BACKGROUND

Bed rest has historically been used as a therapy for the control of several chronic diseases having a high incidence in the elderly population (7, 14, 19). It is also a common step in the process of physical activity reduction leading up to death. Bed rest, induced by both intrinsic and extrinsic factors related to ageing, has catastrophic effects on health, triggering a series of comorbidities that aggravate the physical decline of the elderly (5, 13, 16, 17). The harmful consequences of immobility affect the musculoskeletal, cardiopulmonary, and neurological systems, causing muscular atrophy, hypotension, thrombosis, vascular dysfunction and decubitus ulcers (5, 14, 15, 17).

For example, Paul Rousseau (14) described how the complications of bed rest trigger a spiral of events that, starting with immobility, causes a multi-organ deconditioning followed by a further worsening of the disability that originally caused bed rest. Other studies reported how immobility causes a decrease in cardiac output, heart rate, plasma volume, and a reduction in all parameters of pulmonary function (ventilation, tidal volume, maximum ventilatory capacity), leading to a reduced arterial oxygen saturation. Other consequences of bed rest are a reduction in resting metabolism and appetite besides a negative nitrogen balance.

Bed rest in the elderly is associated to a series of dysfunctions affecting the cardiovascular system, central and peripheric haemodynamic. Blood stasis in the large capacitance vessels, together with a reduced blood flow, are cofactors in the elevated risk of having venous thromboembolism (VTE) and decubitus ulcers (5). In order to diminish some of the negative effects of bed rest, passive mobilization of the patient is nowadays a consolidated practice (14), but several studies reported greater improvements in the vascular functionality of chronically immobilized patients caused by spinal cord injury and/or stroke after being treated with Functional Electrical Stimulation (FES) (3, 6, 9, 12). This type of therapeutic approach has been shown to be effective, incrementing the femoral artery diameter, improving resting blood flow and increasing flow mediated vasodilation (FMD) with no particular contraindication or low treatment tolerance being reported in past studies. Moreover, the application of FES had an evident physiological effect on blood flow that was also accompanied by a significant reduction in decubitus ulcers (18) and other complications linked to immobilization (20).

With a different approach, some studies have also verified how specific interventions may prevent and/or reduce immobilization-induced vascular dysfunctions in the bed resting elderly population. The use of anti-decubitus mattresses, the correct positioning and passive physical therapies, have all been successfully utilized in the prevention of decubitus ulcers. The

use of supports that allow a semi-recumbent position and the elastic compression of the lower limbs are effective therapies to reduce the probability of getting VTE and reduce the pooling of blood in the lower extremities (14).

Other studies (1, 2, 11, 12) have also shown how electrostimulation may be an effective intervention in the cure and prevention of the dysfunctions associated to bed rest. Broderick and colleagues (2) demonstrated that electrostimulation of the calf muscle improves venous return and prevents blood stasis in the legs during 4 hours of forced immobilization. Furthermore, bed rest studies that simulate space microgravity proved that electrostimulation is an effective method to prevent the physiological consequences of immobilization (4).

At present, no study has shown if electrostimulation can diminish the negative effects of bed rest in the vascular functions. For this reason, the objective of this study will be to verify if electrostimulation can improve and/or reduce the negative effects of immobility on the vascular functions of the lower limbs in the bed resting elderly.

## **METHODS**

Inclusion criteria: bed rest and walking inability for at least 6 months and no more than 2 years, age > 70 years.

Exclusion criteria: considering the type of intervention and the evaluations that will be performed, we will not include subjects presenting:

- Myocardial infarction (in the last 6 months)
- Symptomatic aortic stenosis
- Acute pulmonary embolism or pulmonary infarction
- Acute non-cardiac pathology that may be aggravated by electrostimulation (i.e. infection, renal insufficiency)
- Left coronary stenosis or equivalent
- Abnormal electrolytes blood concentration
- Atrial fibrillation with uncontrolled ventricular rate
- Cardiac pacemaker and/or defibrillator
- Use of anticoagulant drugs
- Stroke with consequent hemiparesis

The specialized geriatric medical team of the “Fondazione Mazzali di Mantova” will select 20 non-self-sufficient elders (age > 70 years), living temporarily in the nursing home of the foundation. The family members and/or legal caregivers of the residents will receive detailed information about the measurements and the purpose of the study. All the subjects will receive

an electrostimulation treatment on one of the lower limbs, while the contralateral one will only be evaluated but will not receive any treatment, acting as a control.

All the researchers and health care personnel participating in the study declared that they do not present any conflict of interest in the practice of their functions.

All the subjects will be evaluated through tests in order to determine:

- Anthropometric measures of the limbs
- Vascular functionality of the lower limbs through Echo Color Doppler with the Flow Mediated Dilation (FMD) technique with the objective to measure the residual vasodilatory capacity.
- The measurements will be repeated after an 8 months treatment, based on 30 minutes of electrostimulation, 5 days per week.
- The electrostimulation treatment will take place at the subject bed place for a duration of 30 minutes. The stimulation will be carried out with a professional stimulator (Genesy 1200 pro, Globus Italia Treviso). The electrodes will be placed in a balanced manner following the guidelines delineated by Maffiuletti et al. (12) on the lower right or left limb. As outlined in previous studies (2, 10-12), the intensity and the characteristics of the electric current used for the treatment (capillarization programme Genesy 1200 pro, Globus Italia) will be modulated based upon the subject tolerance.
- Treatment suspension criteria: the treatment will be suspended in case it is not tolerated by the patient, and/or it causes an altered psychophysical state that diminishes the residual quality of life.

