## **STATISTICAL PROCEDURES**

A two-way ANOVA for repeated measures will be used to establish differences between groups and limbs. A Bonferroni post-hoc test will be used, when appropriate, to determine group differences.

Mantova, 14/06/2016, The applicant

A handwritten signature in black ink, appearing to read "[name]".

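### The available text states no masking of FMD measurement, so reading error favouring the stimulated leg at 8 months could not be told apart from a treatment effect

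*Combined protocol and SAP*

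**What the plan says.** METHODS lists two assessments. One is "Anthropometric measures of the limbs" and the other is "Vascular functionality of the lower limbs through Echo Color Doppler with the Flow Mediated Dilation (FMD) technique". FMD is therefore the only vascular outcome named. All 20 patients have one leg stimulated, "while the contralateral one will only be evaluated but will not receive any treatment, acting as a control". On timing and setting the section says "The measurements will be repeated after an 8 months treatment, based on 30 minutes of electrostimulation, 5 days per week" and "The electrostimulation treatment will take place at the subject bed place for a duration of 30 minutes". No sham stimulation is described.

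The available text does not say who scans or reads, whether they know the treated leg or the visit, whether diameters are measured manually or automatically, or whether images are stored. The nearest statement is the conflict-of-interest declaration in METHODS, which concerns interests and does not mask anyone.

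3) STUDY BACKGROUND says that "several studies reported greater improvements in the vascular functionality of chronically immobilized patients caused by spinal cord injury and/or stroke" after electrical stimulation, and lists increased FMD among the effects. For bed rest it says that "no study has shown if electrostimulation can diminish the negative effects of bed rest in the vascular functions".

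STATISTICAL PROCEDURES gives one sentence on the main analysis: "A two-way ANOVA for repeated measures will be used to establish differences between groups and limbs". It does not name the deciding contrast.

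**The concern.** Treatment is visible to ward staff five days a week for 8 months, and nothing in the available text keeps the person who reads the follow-up images from knowing which leg received it. The background reports benefit in other immobilised patients, so an expectation that the treated leg will look better is plausible, although the plan does not state one for this population. If reading involves judgement, an error in that direction at follow-up has the same form as the effect the trial is looking for. No repeated-measures analysis of the recorded values can separate the two. A positive FMD result would stay open to that explanation, and a masked re-read could test the reading part later only if the images had been kept. Limb anthropometry has the same gap.

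**Working it through.** **Stated figures.** The available text gives no alpha, power, effect size, SD or reading error, so there is no planned figure to reproduce.

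**Inputs from METHODS.** 20 patients; two legs per patient; two visits (baseline and 8 months).

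**Assumed inputs.** The contrast (difference in change between legs); a paired t-test on it, which equals the leg-by-visit test in a 2 × 2 within-patient ANOVA; two-sided alpha of 5%; bias b of 0.1 to 0.5 SD of the paired difference in change; 16 completers as a second sample size.

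**Step 1: where the error goes.** Let T and C be the treated and control legs, 0 and 8 the visits, δ the true effect and e the mean error in each cell.

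D = (T8 − T0) − (C8 − C0)

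E[D] = δ + (eT8 − eT0) − (eC8 − eC0)

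With no true effect (δ = 0), the shift under three error patterns and three possible contrasts is:

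| Error pattern | Difference in change | Legs compared at 8 months only | Limb main effect (mean of both visits) |
|---|---|---|---|
| b in treated leg at 8 months only | b | b | b/2 |
| b in both legs at 8 months | 0 | 0 | 0 |
| b in treated leg at both visits | 0 | b | b |

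Error tied to both leg and visit survives in all three contrasts. Constant error in the treated leg cancels only in the difference in change.

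**Step 2: illustration of the consequence.** With b in SDs of D, the t statistic has noncentrality b√n on n − 1 degrees of freedom. For n = 20 and b = 0.3 this is 0.3 × √20 = 1.34; for n = 16 it is 0.3 × √16 = 1.20. Two-sided rejection rates with no true effect:

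| b (SD of D) | n = 20 | n = 16 |
|---|---|---|
| 0 | 5.0% | 5.0% |
| 0.1 | 7.1% | 6.6% |
| 0.2 | 13.6% | 11.6% |
| 0.3 | 24.7% | 20.3% |
| 0.5 | 56.5% | 46.5% |

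For a fixed b the rate rises with n, so small sample size is not the problem here.

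**Step 3: check by simulation (n = 20, b = 0.3, difference in change).** Error in the treated leg at 8 months only: 24.6% rejection. Same error in both legs at 8 months: 4.9%. Same error in the treated leg at both visits: 5.2%. This agrees with the algebra in Step 1.

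**The case against.** The strongest reply is that this argues from silence. The available text starts at heading 3), so who scans and reads could be set out in the sections before it. A reader might infer that the assessors know the treated leg, or that the FMD results will be biased. The documents support neither; they show only that no safeguard is stated in the available text. Nor do they show how far reading depends on judgement. The reference list includes a methods paper on ultrasound assessment of FMD (item 8) that the available text never cites. Its content cannot be seen, so it helps neither side.

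A second reply is that the rates in the working rest on an assumed bias with no link to FMD units, so nobody can say whether 0.3 SD is realistic. That is correct. It would be wrong to read 25% as this trial's false-positive rate, or to put a figure on how much masked reading lowers it. The direction comes from the algebra alone.

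Third, the cancellation depends on the contrast. This stands: under a limb main effect or an 8-month-only comparison, constant error in the treated leg would also count. The unnamed contrast is a separate gap in STATISTICAL PROCEDURES.

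Fourth, coded reading has limits. It does not reach image acquisition, and a reader who recognises a leg is no longer masked if the treated side is predictable; METHODS says only that it is the right or the left. A separate reader or sonographer might seem to be required, but the team is not described and this could need extra staff. What remains untouched is that the plan as written states no protection for its only named vascular outcome, and that a low-cost one is available.

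**Conclusion.** The point holds as an inexpensive improvement that the sponsor should make. No masking of FMD measurement is stated in the available text, one leg is openly treated, and reading error favouring that leg at 8 months shifts the difference in change by its full amount. The size of such error is unknown. The illustrative rates depend on assumed bias, alpha, test and contrast, and they support the direction of the problem only. The conclusion does not depend on bias having occurred, on any expectation held by the assessors, or on the number of patients. It would fall away if the unseen sections already provide masked reading.

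**What to change.** In METHODS, after the FMD item, add:

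> The images of each complete FMD examination (resting and post-stimulus images of one leg at one visit, kept together) are checked for quality at acquisition and stored under a code that hides patient, leg and visit. The code is held by an existing team member who does not read the images. All examinations are read in random order after the last 8-month visit by the study's own reader, and the code is broken only after the FMD values are locked. Scanning and limb anthropometry follow the same fixed procedure for both legs, and those measuring are not told the treated leg where the existing team allows.

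The unit that is coded and shuffled must be the complete examination. FMD compares resting with post-stimulus images, and separating them could add measurement error.

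The plan is dated 14/06/2016, and the text does not show whether scanning has begun. If some baseline examinations are already done, read the stored images in the same way. If baseline images were not stored, still read the 8-month examinations masked to treated leg and report the limitation.

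Cost: file coding and storage (assumed possible, since storage is not described), a key holder from the existing team, a quality check at each scan with a possible repeat, and no FMD values until the end of the trial. No additional study visit is planned. Bias at reading is reduced, and would be removed only if the reader cannot recognise the images. Bias at scanning and in anthropometry is only partly reduced.

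### No rule is stated for choosing which leg is stimulated, although the other leg is the only control; side should be allocated at random and concealed

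*Combined protocol and SAP*

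**What the plan says.** METHODS gives every resident "an electrostimulation treatment on one of the lower limbs, while the contralateral one will only be evaluated", and names that untreated leg as the control. The section plans 20 residents and describes no separate control group.

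The side appears only in the description of the stimulation: "on the lower right or left limb". The nearest wording to an allocation rule is "The electrodes will be placed in a balanced manner following the guidelines", whose subject is the electrodes.

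On timing, "The measurements will be repeated after an 8 months treatment", so each leg is measured at baseline and at 8 months.

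STATISTICAL PROCEDURES says: "A two-way ANOVA for repeated measures will be used to establish differences between groups and limbs". It does not name time as a factor, and the groups it mentions are not defined.

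**The concern.** Using the other leg as control removes differences between people. It does not remove differences between the two legs of one person. Only the rule for choosing the treated leg can do that, and none is given. The documents do not say that staff choose the leg, but nothing prevents it. The choice could follow the leg's condition, its tolerance of the current, ease of access at the bedside, or the baseline FMD itself.

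The consequence depends on the unstated rule and on an analysis that is also unsettled:

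- Choice on the measured baseline FMD biases a test on change through regression to the mean.
- Choice of a lastingly worse leg does not inflate a test on change in the model used below, but it leaves the legs unequal at baseline and biases a comparison at 8 months alone.
- Choice for access, if unrelated to FMD and its expected course, adds no bias.

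At stake is the study's only treatment contrast. A gain in the stimulated leg could come partly from how that leg was picked, and a real gain could be hidden.

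**Working it through.** **Search for a rule.** Study background, METHODS and STATISTICAL PROCEDURES contain no mention of randomisation, alternation, limb dominance, an allocation list, concealment or who decides the side. The remark about balance concerns electrode placement under a cited guideline. Even if read as balancing right and left across residents, it gives no method and no concealment.

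**Inputs.** From the documents: 20 residents, one treated and one control leg each, measured at baseline and 8 months. Assumed: no true effect, a two-sided 5% test, and a between-visit correlation *r* of the leg difference of 0.3, 0.5, 0.7 or 0.9. The plan gives no power calculation or standard deviation, so it has no figure of its own to reproduce.

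**Model.** The right-minus-left difference at each visit is a lasting part (variance *r*) plus independent visit error (variance 1 − *r*), with total SD 1. Bias is in SDs of this leg difference; positive favours the treated leg.

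**Closed forms for the mean bias**, using √(2/π) = 0.798:

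- Lower measured baseline always treated. The mean treated-minus-control difference is −0.798 at baseline and −0.798*r* at 8 months, so the spurious gain in change is 0.798(1 − *r*). At *r* = 0.5 this is 0.798 × 0.5 = 0.40.
- Lastingly worse leg always treated. The mean difference is −0.798√*r* at both visits, so the bias in change is zero. At 8 months alone, with *r* = 0.5, it is −0.798 × 0.707 = −0.56.
- Lastingly worse leg, change regressed on the baseline difference. The intercept is −0.798√*r* × (1 − *r*)/(1 − 2*r*/π). At *r* = 0.5 this is −0.564 × 0.5/0.682 = −0.41.

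| Side chosen by | Analysis | Bias at *r* = 0.3 / 0.5 / 0.7 / 0.9 |
|---|---|---|
| Lower measured baseline, always | Change | 0.56 / 0.40 / 0.24 / 0.08 |
| | 8 months alone | −0.24 / −0.40 / −0.56 / −0.72 |
| Lastingly worse leg, always | Change | 0 / 0 / 0 / 0 |
| | 8 months alone | −0.44 / −0.56 / −0.67 / −0.76 |
| | Baseline-adjusted | −0.38 / −0.41 / −0.36 / −0.18 |

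**False-positive rates.** These come from 100,000 simulated null trials of 20 residents per *r*. The tests are a one-sample t-test on the change in the treated-minus-control difference, the same test on the 8-month difference alone, and the intercept from regressing change on the baseline difference.

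| Side chosen by | Analysis | Rejection at *r* = 0.3 / 0.5 / 0.7 / 0.9 |
|---|---|---|
| Random | Change | 0.049 / 0.049 / 0.051 / 0.050 |
| Lower measured baseline, always | Change | 0.624 / 0.456 / 0.280 / 0.119 |
| | 8 months alone | 0.182 / 0.455 / 0.821 / 0.997 |
| | Baseline-adjusted | 0.050 / 0.049 / 0.049 / 0.050 |
| Lower measured baseline in half, random in the rest | Change | 0.182 / 0.141 / 0.104 / 0.067 |
| Lastingly worse leg, always | Change | 0.050 / 0.051 / 0.050 / 0.051 |
| | 8 months alone | 0.538 / 0.832 / 0.977 / 1.000 |
| | Baseline-adjusted | 0.352 / 0.425 / 0.399 / 0.212 |

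A random side also holds the 8-month and baseline-adjusted tests at about 5%. The adjustment that repairs the first kind of selection fails under the second. The unadjusted change test does the reverse. Only a random side makes all three valid.

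**The case against.** An unstated rule is not the same as a non-random one. The documents nowhere say that FMD guides the choice, or that baseline FMD is read before the side is set. The pages before the study background were not available, so a rule may stand there. **This stands** as a limit: the finding is that no rule is stated in the available text, and an existing random rule would only need to be written in.

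The highest rates need selection on measured FMD in all 20 residents. With such selection in half of them, the rate is about 18% at *r* = 0.3 and close to nominal at *r* = 0.9. Only this kind of selection, with an unadjusted change test, manufactures an apparent benefit; the 8-month biases run against the treated leg. **This also stands.** The rates are conditional, and the full-selection figures are an upper illustration. But bias against the treatment is still bias, and the direction cannot be known without the rule.

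METHODS excludes stroke with hemiparesis, which removes one obvious source of asymmetry between the legs. That lowers the risk, but other asymmetries remain.

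The lack of a time factor in STATISTICAL PROCEDURES is a separate defect. That is fair, but it bears on this point because the effect of a selected side depends on which comparison is made.

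Finally, blocking is not needed for validity. Simple 1:1 randomisation of 20 residents gives a split of 15:5 or worse with probability 0.041, and 14:6 or worse with 0.115. Small fixed blocks could make later sides predictable where staff see which leg is stimulated. **Blocking is therefore optional.**

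**Conclusion.** The concern holds. The available text gives no method for choosing the treated leg, and the untreated leg is the only control. This must be fixed because the study's single contrast depends on it and no analysis chosen afterwards is safe under every selection rule.

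The size of any bias is unknown. Under the model above, the false-positive rate of a change test runs from about 5% (random side, or a lastingly worse leg) to 62% (full selection on measured baseline FMD at *r* = 0.3). These figures rest on assumed correlations and selection rules. They are not a forecast of what will happen in this study.

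**What to change.** Add to METHODS: *The side to be stimulated (right or left) is allocated at random 1:1 from a computer-generated list held by someone not involved in recruitment or FMD measurement. It is revealed only after the baseline FMD of both legs is recorded. Limbs are analysed as allocated.*

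Blocks may be used to keep the sides even; if so, staff should not know the block sizes. If a random rule already exists, it should be stated in these terms.

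The cost is a list for 20 residents and a few protocol sentences. The one downside is that staff can no longer choose the more convenient leg.

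### The suspension rule has no precautionary pause for a new acute illness that the plan itself says electrostimulation may aggravate

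*Combined protocol and SAP*

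**What the plan says.** Three parts of METHODS in the combined protocol and SAP bear on this.

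- **Exclusion criteria.** The list opens with "considering the type of intervention and the evaluations that will be performed, we will not include subjects presenting". One of its ten items reads "Acute non-cardiac pathology that may be aggravated by electrostimulation (i.e. infection, renal insufficiency" (closing bracket omitted here). It is the only item that says stimulation itself may make the condition worse.
- **Treatment schedule.** "The measurements will be repeated after an 8 months treatment, based on 30 minutes of electrostimulation, 5 days per week". The current's intensity and characteristics "will be modulated based upon the subject tolerance".
- **Treatment suspension criteria.** Treatment is "suspended in case it is not tolerated by the patient, and/or it causes an altered psychophysical state that diminishes the residual quality of life". No other suspension rule appears in the text available for review.

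STUDY BACKGROUND adds context on both sides. It describes bed rest in older people as "triggering a series of comorbidities that aggravate the physical decline of the elderly". It also says functional electrical stimulation has been used "with no particular contraindication or low treatment tolerance being reported in past studies".

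**The concern.** The entry criterion is preventive: it keeps stimulation away from a resident with an acute infection or renal insufficiency before anything goes wrong. The reason for it, possible aggravation, is the same in month 3 as on day 0. Once treatment has started, however, the written triggers act only after the resident fails to tolerate treatment or the treatment has produced a state that lowers quality of life.

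What is at stake is the interval between the diagnosis of a new illness and any visible worsening. In that interval a resident can carry a hazard that the plan names and still meet neither written trigger. New illness is foreseeable in non-self-sufficient residents over 70 who are followed for 8 months, given what the background says about comorbidities, although the background names neither infection nor renal insufficiency.

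**Working it through.** The plan states no figure on this point, so there is none to reproduce. The main check sets the provisions side by side. The arithmetic that follows only prices the proposed pause.

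**1. Which provision acts when**

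| Provision (METHODS) | When it acts | Does a new diagnosis alone trigger it? |
|---|---|---|
| Exclusion criteria | At inclusion | No; it governs who enters |
| Adjustment of current to tolerance | During treatment | No; it follows tolerance |
| Suspension, first trigger | During treatment, once not tolerated | No |
| Suspension, second trigger | During treatment, once an altered state exists and the treatment caused it | No |

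The remaining available text has no re-check of eligibility, no pause-and-restart rule and no monitoring schedule for new acute illness. STATISTICAL PROCEDURES does not touch the point.

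**2. Planned exposure**

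Inputs from METHODS: 8 months, 5 sessions a week, 30 minutes each, 20 residents. Assumption: 30.44 days per month.

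- Weeks: 8 × 30.44 / 7 = 34.8
- Sessions per resident: 34.8 × 5 = 173.9, about 174 (about 87 hours at half an hour each)
- Sessions in the trial: 173.9 × 20 = about 3,479

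**3. Cost of a pause to one resident**

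The length of a pause is not in the documents; 1, 2 and 4 weeks are assumed.

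| Pause | Sessions lost | Hours lost | Share of 173.9 |
|---|---|---|---|
| 1 week | 5 | 2.5 | 2.9% |
| 2 weeks | 10 | 5 | 5.7% |
| 4 weeks | 20 | 10 | 11.5% |

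**4. Cost of pauses to the trial**

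The number of residents paused is also assumed. With 2 weeks (10 sessions) each:

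- 2 residents: 20 / 3,479 = 0.6%
- 5 residents: 50 / 3,479 = 1.4%
- 10 residents: 100 / 3,479 = 2.9%

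These figures measure what the safeguard would cost. They do not measure the hazard: a pause runs from diagnosis to resolution, the unprotected interval runs from diagnosis to visible worsening, and the documents give neither duration.

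**The case against.** The strongest reply is that the written protection is wider than it looks and that the staff would stop anyway. Not being tolerated need not mean only the sensation of the current; medical intolerance is a fair reading. The current can be reduced, the suspension list is not said to be complete, and nothing orders staff to continue. A specialised geriatric team selects the residents, and the background cites good tolerability.

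Part of this stands. The plan does not forbid a precautionary stop, and aggravation that lowers quality of life can meet the second trigger. But even on the wide reading each trigger waits for worsening. The team's only documented role is to select residents; a decision to pause is not assigned to it. The tolerability statement concerns patients immobilised by spinal cord injury and/or stroke, and the plan wrote the exclusion despite that literature.

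A second objection concerns scope. The exclusion list as a whole is justified by both the intervention and the evaluations, so a new myocardial infarction or pulmonary embolism might seem to belong here too. The text does not say which of the two reasons applies to each of the other nine items, and it states a stimulation hazard for none of them. The point is therefore confined to the item where the plan states one.

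A third objection stands in full: because the list also refers to the evaluations, a rule requiring the 8-month vascular test whatever the resident's condition would be unsafe. The fix needs a medical exception.

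A reader might infer that the plan instructs staff to stimulate acutely ill residents, or that residents will be harmed. The documents support neither: the rule is silent on continuation, the exclusion says only that aggravation may occur, and no incidence or harm rate is given.

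**Conclusion.** The point holds as a minor patient-safety gap. For infection and renal insufficiency the plan states a hazard and guards against it at entry. For the following 8 months the available text has only triggers that act on intolerance or on an effect already caused by treatment. Applied exactly as written, they leave the 5-days-a-week schedule uninterrupted in a resident newly diagnosed with the named hazard.

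The size of the hazard cannot be stated. No estimate, test or sample size is affected, and it would be wrong to infer that the trial's result is biased by this omission.

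Confidence is medium. The conclusion rests on the available text, which begins at section 3; the earlier pages were removed before review and could contain a further rule, so absence from the whole plan is not claimed. It also assumes that the suspension criteria are followed as written, without unrecorded clinical discretion.

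**What to change.** Add to the treatment suspension criteria in METHODS:

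> Stimulation is also suspended when the geriatric team diagnoses an acute pathology that electrostimulation may aggravate (e.g. infection, renal insufficiency), and resumes when the team records that it has resolved. Missed sessions are recorded, and both legs are still measured at 8 months unless the team judges the test medically inadvisable, in which case it is deferred until safe.

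The trigger is the diagnosis, so no scheduled chart review or extra staff is needed. Measuring both legs keeps a safety pause from turning into missing outcome data, while the exception leaves the test to medical judgement.

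The cost is two sentences, one recorded decision to suspend and one to resume per diagnosis, and about 5 of 174 planned sessions (2.9%) for each week that a resident is paused. Some 8-month measurements may be taken late. Which illnesses count, and when they have resolved, stay with the team; the change makes that decision explicit and recorded.
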